9.2 Informed Consent Process

Informed consent is a process that is initiated prior to an individual agreeing to participate in a trial and continuing throughout the individual's trial participation. Before any study procedures are performed, informed consent will be obtained and documented. Subjects will receive a concise and focused presentation of key information about the clinical trial, verbally and with a written consent form. The explanation will be organized, and presented in lay terminology and language that facilitates understanding why one might or might not want to participate.

An investigator or designee will describe the protocol to potential subjects face-to-face. The key information about the purpose of the study, the procedures and experimental aspects of the study, risks and discomforts, any expected benefits to the subject, and alternative treatment will be presented first to the subject.

Subjects will also receive an explanation that the trial involves research, and a detailed summary of the proposed study procedures and study interventions/products. This will include aspects of the trial that are experimental, the probability for random assignment to treatment groups, any expected benefits, all possible risks (including a statement that the particular treatment or procedure may involve risks to the subject or to the embryo or fetus, if the subject is or may become pregnant, that are currently unforeseeable), and the expected duration of the subject's participation in the trial.

Subjects will be informed that they will be notified in a timely manner if information becomes available that may be relevant to their willingness to continue participation in the trial. Subjects will receive an explanation as to whether any compensation and any medical treatments are available if injury occurs, and, if so, what they consist of, or where further information may be obtained. Subjects will be informed of the anticipated financial expenses, if any, to the subject for participating in the trial, as well as any anticipated prorated payments, if any, to the subject for participating in the trial. They will be informed of whom to contact (e.g., the investigator) for answers to any questions relating to the research project.

Information will also include the foreseeable circumstances and/or reasons under which the subject's participation in the trial may be terminated. The subjects will be informed that participation is voluntary and that they are free to withdraw from the study for any reason at any time without penalty or loss of benefits to which the subject is otherwise entitled.

The extent of the confidentiality of the subjects' records will be defined, and subjects will be informed that applicable data protection legislation will be followed. Subjects will be informed that the monitor(s), auditors(s), IRB, NIAID, and regulatory authority(ies) will be granted direct access to the subject's original medical records for verification of clinical trial procedures and/or data without violating the confidentiality of the subject, to the extent permitted by the applicable laws and regulations, and that, by signing a written informed consent form, the subject is authorizing such access.

Subjects will be informed that records identifying the subject will be kept confidential, and, to the extent permitted by the applicable laws and/or regulations, will not be made publicly available and, if the results of the trial are published, the subject's identity will remain confidential. Subjects will be informed whether private information collected from this research and/or specimens will be used for additional research, even if identifiers are removed.

Subjects will be allowed sufficient time to consider participation in this research trial, and have the opportunity to discuss this trial with their family, friends or legally authorized representative, or think about it prior to agreeing to participate.

ICFs will be IRB-approved and subjects will be asked to read and review the consent form. Subjects must sign the ICF prior to starting any study procedures being done specifically for this trial.

Once signed, a copy of the ICF will be given to the subject(s) for their records. The subject(s) may withdraw consent at any time throughout the course of the trial. The rights and welfare of the subject(s) will be protected by emphasizing to them that the quality of their medical care will not be adversely affected if they decline to participate in this study.

Study personnel may employ recruitment efforts prior to obtaining study consent if a patient-specific screening consent is on record or if the IRB has agreed that chart review is allowed without a fully executed screening consent. In cases where there is not a patient-specific screening consent on record, site Clinical staff may pre-screen via chart review and refer potential subjects to the Research staff. Research staff would obtain written consent per the standard informed consent process before conducting protocol-specific screening activities.

New information will be communicated by the site PI to subjects who consent to participate in this trial in accordance with IRB requirements. The informed consent document will be updated and subjects will be re-consented per IRB requirements, if necessary. Subjects will be given a copy of all ICFs that they sign.

Human Genetic Testing

No human genetic testing will be performed in this study.

9.3 Consent for Future Use of Stored Specimens and Data

Residual samples/specimens and data are those that are left over after protocol-specified testing and this study has been completed. Subjects will be asked for permission to keep any data and any remaining (residual) specimens (serum and PBMCs) derived from venous blood samples, swabs and other mucosal samples for possible use in future research studies, such as examining additional immunological assessments or testing for antibodies against other viruses or bacteria. These residual specimens will be stored coded indefinitely at a DMID-contracted storage facility. Data or specimens may be shared with investigators at the participating site and with other investigators at U.S. or international institutions. The recipients of data or specimens will be informed that these specimens have a NIH certificate of confidentiality. The information provided to a recipient will not contain direct identifiable information. Use of the specimens will require a new protocol and review and approval of that protocol and the specimens for use by an IRB.

There are no benefits to subjects in the collection, storage and subsequent future use of their data/samples/specimens. These data/samples/specimens will not be sold or used directly for production of any commercial product. The data/sample/specimen will be encoded (labeled) only with a barcode and a unique tracking number that connects to a code key at the study site. Restricted access to the code key is maintained by the principal investigator to protect subject confidentiality. Reports from future research studies performed using subjects' data/samples/specimens will NOT be kept in their health records.

Subjects may be given the option to decide if they want their **residual** specimens with their data to be used for future research or have these specimens destroyed at the end of this trial. The subject's decision can be changed at any time by notifying the study doctors or nurses in writing. However, if the subject originally consents to the future use of **residual** specimens with their data and subsequently changes his/her decision, any data already collected from a previously collected specimen may still be used for future research.

9.4 Exclusion of Women, Minorities, and Children (Special Populations)

This trial will include all healthy adults who meet the inclusion/exclusion criteria, regardless of religion, sex, or ethnic background. Only subjects, aged 18 to 49 years inclusive, will be included. This age range was selected to represent the population with the highest incidence of gonorrhea therefore children are excluded from this study. Special populations, e.g., non-English speakers, illiterate or non-writing individuals, and vulnerable populations, for which no benefit of trial participation has been identified, will not be enrolled in this trial.

9.5 Subject Confidentiality

Subject confidentiality is strictly held in trust by the participating investigators, their staff, and the sponsor(s) and their agents. This confidentiality includes documentation, investigation data, subject's clinical information, and all other information generated during participation in the study. No information concerning the study or the data generated from the study will be released to any unauthorized third party without prior written approval of the DMID and the subject. Subject confidentiality will be maintained when study results are published or discussed in conferences. The study monitor or other authorized representatives of the sponsor or governmental regulatory agencies may inspect all documents and records required to be maintained by the investigator, including but not limited to, medical records (office, clinic, or hospital) and pharmacy records for the subjects in this study. The clinical study site will permit access to such records.

All records will be kept locked and all computer entry and networking programs will be carried out with coded numbers only and with password protected systems. All non-clinical specimens, evaluation forms, reports, and other records that leave the site will be identified only by a coded number.

9.6 Certificate of Confidentiality

To protect privacy, we have received a Certificate of Confidentiality. With this Certificate, the researchers cannot be forced to release information that may identify the research subject, even by a court subpoena, in any federal, state, or local civil, criminal, administrative, legislative, or other proceedings. The researchers will use the Certificate to resist any demands for information that would identify the subject, except as explained below.

The Certificate cannot be used to resist a demand for information from personnel of the United States Government that is used for auditing or evaluation of federally funded projects, like this study, or for information that must be released in order to meet the requirements of the FDA.

A Certificate of Confidentiality does not prevent the subject from voluntarily releasing information about themselves or their involvement in this research. If any person or agency obtains a written consent to receive research information, then the researchers may not use the Certificate to withhold that information.

The Certificate of Confidentiality does not prevent the researchers from reporting without the subject's consent, information that would identify the subject as a participant in the research project regarding matters that must be legally reported including: child and elder abuse, sexual abuse, or wanting to harm themselves or others.

The release of individual private information or specimens for other research will only occur if consent was obtained from the individual to whom the information, document, or biospecimen pertains, *or* for the purposes of other research that is in compliance with applicable Federal regulations governing the protection of human subjects in research.

9.7 Costs, Subject Compensation, and Research Related Injuries

There is no cost to subjects for the research tests, procedures, and study product while taking part in this trial. Procedures and treatment for clinical care may be billed to the subject, subject's insurance or third party. Subjects may be compensated for their participation in this trial.

Compensation will be in accordance with the local IRB's policies and procedures, and subject to IRB approval.

If it is determined by the site PI that an injury occurred to a subject as a direct result of the tests or treatments that are done for this trial, then referrals to appropriate health care facilities will be provided to the subject. Study personnel will try to reduce, control, and treat any complications from this trial. Immediate medical treatment may be provided by the participating site. No financial compensation will be provided to the subject by the NIAID, NIH to the subject by the participating site for any injury suffered due to participation in this trial.

10 STATISTICAL CONSIDERATIONS

10.1 Study Hypotheses

The primary goal of this study is to assess the systemic and mucosal immunogenicity of two doses of 4CMenB compared to a placebo comparator. A secondary goal is to assess the safety and reactogenicity of 4CMenB. Though the study is not designed to formally test any hypotheses, p-values may be reported that compare the immunogenicity and/or safety data between treatment groups. The null hypotheses for these tests will be that there is no difference between treatment groups and the alternative hypotheses will be two-sided.

10.2 Sample Size Considerations

A total of approximately 50 (maximum of 60), subjects will be enrolled and randomized to one of two study arms based on a 4:1 allocation ratio to the 4CMenB arm and placebo arm, respectively. The 4:1 allocation ratio was not selected based on any formal statistical criteria but instead was selected to maximize the number of subjects administered 4CMenB, and thus maximize the amount of immunogenicity data collected on subjects administered 4CMenB. Of the approximate 50 subjects, approximately 20 subjects will be enrolled into the Rectal Mucosal Biopsy Cohort. As with the overall sample size, this number was not selected based on any statistical criteria but was selected weighing the feasibility of enrolling subjects who would consent to the biopsy procedure against ensuring ample data was collected via rectal mucosal biopsy as there are no data on the impact of 4CMenB on immunologic responses at the human mucosal surfaces where GC is typically encountered.

The study is not designed to formally test any hypotheses associated with the immunogenicity data. Using the ELISA GMT estimates reported in [Table 2](#) of Semchenko et al.,¹³ estimated GMT 95% confidence intervals were calculated for the 4CMenB group using the post-vaccination estimates and for the placebo group using the pre-vaccination estimates. [Table 2](#) provides the estimated GMTs and GMT ratios between groups. To account for a small percentage of the approximate 50 randomized subjects not being eligible for the primary analysis (e.g., due to not having immunogenicity data available), a range of sample sizes from 36 to 50 was explored.

Table 2: 95% Confidence Intervals for GMTs and GMT Ratios across a range of Sample Sizes and Antigens

| N (Vaccine / Placebo) | Antigen ^a | Treatment Group | GMT Estimate | GMT 95% CI | GMT Ratio | GMT Ratio 95% CI |
|-----------------------------|----------------------|--------------------|-----------------|-----------------|--------------|---------------------|
| 30 / 6 | Ng OMV | Vaccine | 42224 | 35234, 50601 | 1.23 | 0.77, 1.97 |
| | | Placebo | 34297 | 16638, 70697 | | |
| | Ng whole cell | Vaccine | 78793 | 61639, 100721 | 1.62 | 0.86, 3.05 |
| | | Placebo | 48503 | 19329, 121713 | | |
| | Nm whole cell | Vaccine | 388023 | 262806, 572900 | 4.00 | 1.53, 10.47 |
| | | Placebo | 97006 | 29287, 321311 | | |
| | Ng rNHBA | Vaccine | 1176267 | 876783, 1578046 | 34.3 | 16.98, 69.26 |
| | | Placebo | 34297 | 16638, 70697 | | |
| 35 / 8 | Ng OMV | Vaccine | 42224 | 35748, 49873 | 1.23 | 0.81, 1.87 |
| | | Placebo | 34297 | 19275, 61026 | | |
| | Ng whole cell | Vaccine | 78793 | 62863, 98760 | 1.62 | 0.93, 2.83 |
| | | Placebo | 48503 | 23305, 100944 | | |
| | Nm whole cell | Vaccine | 388023 | 271134, 555305 | 4.00 | 1.73, 9.26 |
| | | Placebo | 97006 | 37363, 251856 | | |
| | Ng rNHBA | Vaccine | 1176267 | 897654, 1541356 | 34.3 | 18.63, 63.14 |
| | | Placebo | 34297 | 19275, 61026 | | |
| 40 / 10 | Ng OMV | Vaccine | 42224 | 36161, 49303 | 1.23 | 0.85, 1.79 |
| | | Placebo | 34297 | 20947, 56156 | | |
| | Ng whole cell | Vaccine | 78793 | 63850, 97233 | 1.62 | 0.98, 2.68 |
| | | Placebo | 48503 | 25906, 90811 | | |
| | Nm whole cell | Vaccine | 388023 | 277922, 541742 | 4.00 | 1.88, 8.51 |
| | | Placebo | 97006 | 42880, 219456 | | |
| | Ng rNHBA | Vaccine | 1176267 | 914549, 1512881 | 34.3 | 19.85, 59.27 |
| | | Placebo | 34297 | 20947, 56156 | | |

a: From Semchenko (2018), [Table 2](#). Vaccine group estimates are derived from the post-vaccination estimates and placebo group estimates are derived from the pre-vaccination estimates.

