6.7. Multiple Comparisons/Multiplicity

There is only one primary endpoint at 5 timepoints. No formal hypothesis test of the primary outcome will be performed. No adjustments for multiple comparison are planned. No adjustment to the alpha level for CIs will be performed.

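### Protocol Table 2 builds its GMT-ratio intervals on an unstated common SD that its own arm intervals contradict; under those arm SDs the Ng OMV and Ng whole cell ratio intervals are too narrow

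*Protocol*

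**What the plan says.** Protocol 10.2 takes titer estimates from a cited study, using post-vaccination values for the 4CMenB arm and pre-vaccination values for the placebo arm. Table 2 then shows, for four antigens at 30/6, 35/8 and 40/10, a 95% CI for each arm's GMT and a 95% CI for the ratio. Neither the text nor the footnote gives an SD, an interval formula or an equal-variance assumption. SAP section 5 does not repeat the table.

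The rows that matter most at 40/10:

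- Ng OMV: "Ng OMV | Vaccine | 42224 | 36161, 49303 | 1.23 | 0.85, 1.79", with "Placebo | 34297 | 20947, 56156".
- Ng whole cell: "Ng whole cell | Vaccine | 78793 | 63850, 97233 | 1.62 | 0.98, 2.68", with "Placebo | 48503 | 25906, 90811".
- Ng rNHBA: "Ng rNHBA | Vaccine | 1176267 | 914549, 1512881 | 34.3 | 19.85, 59.27". Its placebo row is identical to the Ng OMV placebo row.

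At 30/6 the Ng OMV row reads "Ng OMV | Vaccine | 42224 | 35234, 50601 | 1.23 | 0.77, 1.97".

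Two statements limit the table's role. Of the biopsy-cohort size, Protocol 10.2 says: "As with the overall sample size, this number was not selected based on any statistical criteria". SAP 6.7 says: "No formal hypothesis test of the primary outcome will be performed".

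**The concern.** The two interval columns rest on different variance models. The arm column lets each arm have its own SD. The ratio column imposes one SD on both. A reader who takes the arm intervals at face value cannot arrive at the ratio intervals beside them without guessing that variances were pooled.

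The choice matters under roughly 4:1 allocation. Pooling weights each arm's variance by its degrees of freedom, so the large arm dominates. The variance of the log ratio, however, is dominated by the small arm. When the small arm also has the larger SD, the pooled standard error is too small.

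At stake is how much between-arm precision the trial is said to offer. Table 2 is the only such statement in either document. GC OMV is the antigen class of the primary and first secondary endpoints, and both objectives are framed as comparisons with placebo.

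**Working it through.** All calculations are on the natural-log scale; the only inputs are the figures in Table 2.

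**Step 1: arm SDs.** SD = [ln(U/L)/2] × √n / t(0.975, n−1).

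- Ng OMV vaccine, n = 40: [ln(49303/36161)/2] × √40 / 2.023 = 0.485.
- Ng OMV placebo, n = 10: [ln(56156/20947)/2] × √10 / 2.262 = 0.689.

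The same SDs come back at all three sample sizes, so the arm column uses arm-specific SDs with t quantiles.

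| Antigen | Vaccine SD | Placebo SD |
|---|---|---|
| Ng OMV | 0.485 | 0.689 |
| Ng whole cell | 0.658 | 0.877 |
| Nm whole cell | 1.043 | 1.141 |
| Ng rNHBA | 0.787 | 0.689 |

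**Step 2: reproduce the stated ratio interval.** Ng OMV at 40/10:

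- Pooled SD = √[(39 × 0.485² + 9 × 0.689²)/48] = 0.529.
- SE = 0.529 × √(1/40 + 1/10) = 0.187.
- Half-width = t(0.975, 48) × SE = 2.011 × 0.187 = 0.376.
- Ratio = 42224/34297 = 1.231, so the interval is 1.231 × exp(±0.376) = 0.85 to 1.79, as stated.

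The same formula reproduces all 12 ratio intervals to two decimals. Seven other constructions did not reproduce the table: pooled with z, simple-average variance, vaccine SD only, unpooled with z, unpooled with n1+n2−2 df, Welch, and the smaller arm's df.

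**Step 3: the conflict across antigens.** Ng OMV and Ng rNHBA share one placebo row (arm SD 0.689). In the ratio column that arm is given an SD of 0.529 for Ng OMV and √[(39 × 0.787² + 9 × 0.689²)/48] = 0.770 for Ng rNHBA.

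**Step 4: unequal-variance (Welch) interval from the same SDs.** Ng OMV at 40/10:

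- SE = √(0.485²/40 + 0.689²/10) = 0.231, with Satterthwaite df 11.3 and t = 2.193.
- Half-width = 2.193 × 0.231 = 0.507, giving 0.74 to 2.04.
- 0.507/0.376 = 1.35, so 35% wider on the log scale.
- Placebo share of the variance: (0.689²/10)/0.231² = 0.89. Vaccine weight in the pooled variance: 39/48 = 0.81.

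| Antigen | N | Stated | Welch | Wider (log scale) |
|---|---|---|---|---|
| Ng OMV | 40/10 | 0.85-1.79 | 0.74-2.04 | 35% |
| Ng OMV | 35/8 | 0.81-1.87 | 0.69-2.21 | 41% |
| Ng OMV | 30/6 | 0.77-1.97 | 0.60-2.53 | 53% |
| Ng whole cell | 40/10 | 0.98-2.68 | 0.85-3.10 | 29% |
| Ng whole cell | 35/8 | 0.93-2.83 | 0.77-3.43 | 35% |
| Ng whole cell | 30/6 | 0.86-3.05 | 0.65-4.07 | 45% |

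Nm whole cell widens by 13-25%. Ng rNHBA, where the larger SD is in the vaccine arm, moves by −2% to +4%.

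**Step 5: coverage.** One million trials per setting were simulated with normal log titers, taking the arm SDs as true.

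| Pooled interval, nominal 95% | 40/10 | 35/8 | 30/6 |
|---|---|---|---|
| Ng OMV | 88.9% | 88.6% | 88.1% |
| Ng whole cell | 90.2% | 90.0% | 89.6% |

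Welch covers 94.5-94.9% throughout. If the true SDs are equal, the pooled interval covers 95.0%, and Welch is on average 5%, 8% and 12% wider at 40/10, 35/8 and 30/6.

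**The case against.** A pooled t interval is a standard two-sample interval, and arm-specific intervals beside a pooled ratio interval are common. The pooled SD is the correct df-weighted average of the two arm SDs, so this is a choice of method and not a miscalculation. That stands. It does not supply the missing statement of method, and it does not make a common SD compatible with the arm column.

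Unequal sample SDs need not mean unequal true variances, and the documents do not give the size of the source study. Assuming equal, independent samples of 10, 20, 30 or 50, an F test of the SDs would give p = 0.31, 0.14, 0.06 or 0.015 for Ng OMV, and 0.41, 0.22, 0.13 or 0.047 for Ng whole cell. This also stands: "too narrow" holds only if the arm SDs are true. The disagreement between the columns does not depend on it.

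The widening is not all due to unequal variances. For Ng OMV at 30/6 the standard error rises by a factor of 1.27 and the t multiplier by 1.20 (2.444/2.032, as df fall from 34 to 6); 1.27 × 1.20 is about 1.53. But the standard error alone matters: an unpooled interval with z, the narrowest unpooled variant, is 0.78-1.94 for Ng OMV at 40/10, still wider than stated.

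Finally, little depends on the table. It did not set the sample size, the SAP plans intervals by arm only, and the inputs are serum titers while the primary endpoint is rectal. All true, and they keep the point minor.

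**Conclusion.** The concern holds. Table 2's ratio intervals come from an unstated pooled variance that contradicts the arm SDs in the same table. Under those SDs, the intervals for Ng OMV and Ng whole cell are too narrow at all three sample sizes: Welch intervals are 29-53% wider on the log scale, and the pooled intervals cover about 88-90% against a nominal 95%. Nm whole cell is mildly affected (pooled coverage about 93.6%); Ng rNHBA is slightly conservative (about 96.6%).

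The size claims assume normal log titers and that the arm SDs, recovered from rounded limits, are the true ones. The finding that the two columns use different variance models needs neither assumption. The practical effect is an optimistic picture of precision, clearest for Ng whole cell at 40/10, where the lower limit moves from 0.98 to 0.85. Intervals that include 1 still do, and those that exclude it still do.

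**What to change.** Recompute the ratio-interval column of Table 2 with the Welch/Satterthwaite interval, using the SDs already behind the arm intervals, and name the method in a footnote. Protocol 10.1 allows between-group p-values without naming a method; use the same unequal-variance approach for any between-arm comparison of log titers reported under it. With allocation near 4:1 this is a safe default.

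The cost is one table column and one footnote, with less favourable stated precision for Ng OMV and Ng whole cell. If the true SDs are equal, the price is the 5-12% extra average width shown above. Enrolment, allocation and the planned SAP tables do not change. At the least, if the sponsor keeps the pooled intervals, the footnote should state the equal-variance assumption and justify it against the arm SDs.
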